#### **Neurovalens Limited**

Identifier: EXP18020 Clinical Study Identifier: 243973

It is likely that some subjects will not utilize their device for the recommended 7, or even mandated 5, hours per week, and therefore a treatment response analysis will be performed which will identify the number of subjects per treatment group who fail to meet these requirements at least once on study. The treatment response analysis will further summarize the frequency of times that the mandated hours are not adhered to by calculating the percentage non-adherence as  $n_t/n_T \times 100$  whereby  $n_t$  is the number of weeks a subject fails to use their device for the mandated 5 hours per week and  $n_T$  is the total number of weeks the subject has been on the study. The treatment response analysis will be used to identify groups of subjects which have high (>75%) , medium (50-75%) and low (<50%) treatment adherence (defined as 100% - percentage non-adherence) and their percentage weight loss will be summarized by treatment and adherence group accordingly, at the 6 month time point.

The total number of hours a subject avails of the mentor support group (WST or CTM) over the course of the subject's study participation will be described using summaries of the categorical time spent per week (0, 0-2, 2-4, 4-6, >6 hours), per treatment group.

## 12.4 Blinding Assessment

For the safety analysis set, a cross tabulation of the number of subjects who received the VeSTAL and sham control devices, against the number of subjects who think they are on 'Sham', 'Active' or who 'Do not know' will be reported for responses provided at baseline, 1 and 6, months. At 6 months this analysis is repeated for the coordinators response as to what device they think the subject is on: 'Sham', 'Active' or 'Do not know'. Both the subjects and coordinators provide reasons for their choice. This information is recorded in a listing.

The assessment will follow the approach outlined by James et al (1996) where an index of blindedness (BI) is created based on a modification of a Kappa statistic to incorporate the 'Do not know' category. The index ranges from 0 to 1 and gives an indication of how good the blind is, where 0 implies complete lack of blinding and 1 implies complete blinding. The weight assigned to the three response options will be 0 for a correct guess, 1 for a 'Do not know' response and 0.75 for an incorrect guess. A table of the actual treatment received against the perceived treatment received showing the numbers and proportions of subjects falling into each of the six categories will be produced alongside the index of blindedness where a result greater than 0.5 indicates a result better than that obtained by random choices. The 95% asymptotic confidence intervals will be included with the interpretation that a suitable level of blindedness has been achieved if the lower bound of the interval is above 0.5. The responses provided at 1 month will take precedence in deciding whether the blinding has been maintained, however should considerable differences exist between responses at each timepoint, further exploratory analysis may be performed, for example to infer whether subject response has an association with device performance or subject adherence.

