### Frequency of Follow-Up Appointments

As shown in the summary of frequency of follow-up appointments for all sites, the subjects will visit in person at: enrollment (0 months); 3 months and 6 months.

Telephone or email follow-up are scheduled once for the 1-month post enrollment timepoints. These follow-up sessions are estimated to take about 10 minutes each and during them the subjects should complete the adverse event questionnaire.

Also, at the 1 month timepoint the subject will be asked which intervention group (i.e. active or sham) they believe they are in and why they believe this (also referred to as a Bliniding Assessment). These data will be gathered by a pop-up question in the VeSTAL study app. The subject and coordinator will not enter into discussion on this matter. These data will be collected and analysed at the end of the study.

Study participants are also free to contact (call or email) study personnel at any time with any issues or inquiries, and there is also the facility to bring subjects in on an ad hoc basis should concerns arise.

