#### **Neurovalens Limited**

Clinical Study Identifier: 243973

Identifier: EXP18020

The study will be randomized using a parallel assignment with a 1:1 allocation between the active VeSTAL device and the sham control. A total of 200 subjects are planned to be recruited across study sites, with a dropout allowance of 10% to generate a minimum of 90 active treatment and 90 control subjects. The anticipated recruitment across the sites are as follows:

- University of San Diego (UCSD) Altman Clinical and Translational Research Institute (ACTRI): a total of 106 subjects who pass through screening and are randomized.
- UCSD Exercise and Physical Activity Resource Center (EPARC; second trial site at UCSD campus): a total of 100 subjects who pass throughs screening and are randomized.
- University of Ulster (UU): a total of 94 subjects who pass through screening and are randomized.
- Texas Diabetes and Endocrinology (TDE): a total of 40 subjects who pass through screening and are randomized.

Data will be collated from all sites and analyzed as one dataset at the 6-month timepoint. The study is planned to last approximately 6 months for each subject, with the subjects given the headset device to use daily in the home environment.

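### SAP 12.4 calls blinding suitable when the lower 95% limit of the James index exceeds 0.5, a rule that can withhold 'suitable' from a sound blind and grant it to a broken one

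*SAP*

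**What the plan says.** SAP 12.4 plans a James blinding index, "based on a modification of a Kappa statistic to incorporate the 'Do not know' category". It runs from 0 (no blinding) to 1 (complete blinding). On the weights it says: "The weight assigned to the three response options will be 0 for a correct guess, 1 for a 'Do not know' response"; an incorrect guess gets 0.75.

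Two statements then use the same number. The section says that "a result greater than 0.5 indicates a result better than that obtained by random choices", and that "a suitable level of blindedness has been achieved if the lower bound of the interval is above 0.5", with a 95% asymptotic interval. On timing: "The responses provided at 1 month will take precedence in deciding whether the blinding has been maintained".

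The section also plans a table of actual against perceived treatment "showing the numbers and proportions of subjects falling into each of the six categories", subject answers at baseline, 1 and 6 months, coordinator answers at 6 months, and a listing of reasons. Exploratory analysis may follow if answers differ considerably between time points. No conclusion is attached to any of these.

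Neither document states an expected share of DK answers. For the 1-month app question, Protocol 6.4 (Frequency of Follow-Up Appointments) says that "the subject will be asked which intervention group (i.e. active or sham) they believe they are in". SAP 12.4 tabulates three answers, including DK.

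**The concern.** If the blind is intact, subjects who name an arm are guessing. Their guesses alone put the index at 0.5, so requiring the lower limit to lie above 0.5 asks for significantly more than an intact blind delivers among guessers. Under an intact blind the excess has to come from DK answers.

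Separately, the index folds two things into one number: how many subjects decline to guess, and how often the rest are right. Many DK answers can offset accurate guessing.

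The question matters in this trial. Protocol 6.14 describes a sham that stimulates for 50 seconds per session and recognises that subjects may notice vestibular stimulation. Protocol section 9 has users settle at a level where they feel a gentle sway. The outcome is weight change on a self-managed diet, which belief about allocation could influence. The 12.4 rule is the only stated criterion for whether the double blind held.

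**Working it through.** **Inputs.** From SAP 12.4: threshold 0.5, weights 0 / 0.75 / 1, 95% asymptotic interval. From SAP section 3: 200 subjects 1:1, "with a dropout allowance of 10% to generate a minimum of 90 active treatment and 90 control subjects". Rates below use 90 per arm, with 100 per arm in brackets because few may have left by month 1. Assumptions: the standard James formula (not printed in the SAP), equal DK shares in both arms, and DK share and guessing accuracy varied because the documents give neither.

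**Formula.** Index = [1 + D + (1 − D) × K] / 2. D is the DK share and K = (observed − expected disagreement) / expected disagreement among guessers. With two arms the 0.75 weight cancels from K.

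**The SAP's own anchors.**
- All correct, no DK: K = (0 − 0.50)/0.50 = −1; index = (1 + 0 − 1)/2 = 0.
- Random guessing, no DK: K = 0; index = (1 + 0 + 0)/2 = 0.5, the SAP's random-choice value.
- Nearly all DK: index close to 1.

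**Threshold.** Under random guessing the index is (1 + D)/2: 0.50, 0.55, 0.60 and 0.65 at 0, 10, 20 and 30% DK. It equals 0.5 only when nobody answers DK. At 0% DK and 180 subjects the standard error is 0.0373, so the estimate must reach about 0.5 + 1.96 × 0.0373 = 0.573, although its expected value is 0.5.

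**Mixing.**
- Perfect blind, 10% DK: (1 + 0.10 + 0)/2 = 0.55.
- 75% of guessers correct, 40% DK: K = (0.25 − 0.50)/0.50 = −0.5; index = (1 + 0.40 − 0.60 × 0.5)/2 = 0.55.

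These two trials differ greatly in blinding but have the same expected index, and each meets the rule about 28% of the time. That equality is a property of the index; any single cut would treat them about alike.

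**Probability that the rule is met** (100,000 simulated trials per cell, delta-method standard error, normal 95% interval; a dash marks a cell not needed here):

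| Correct among guessers | 0% DK | 10% | 20% | 30% | 40% | 50% |
|---|---|---|---|---|---|---|
| 50% (perfect blind) | 3% (3%) | 28% (31%) | 78% (83%) | 98% (99%) | – | – |
| 60% | – | – | 8% (9%) | 59% (64%) | 97% (98%) | – |
| 75% | – | – | – | 0.5% (0.5%) | 28% (31%) | 93% (95%) |

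Along a row, the DK share moves the verdict. Down the 30% column, accuracy moves it just as strongly: 98%, 59%, 0.5%.

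**The case against.** The strongest defence is that DK answers ought to count as evidence of blinding, that a demanding rule puts the burden of proof on the sponsor, and that little turns on the result. Much of this stands. Weight 1 for DK is a legitimate feature of the index. The six-cell table, coordinator answers and listed reasons let a reader see what lies behind the number. No efficacy criterion uses the verdict. A demanding rule also has some merit at low DK: at 60% correct and 20% DK it withholds 'suitable' in 100 − 8 = 92% of trials. But the same rule grants 'suitable' in 93% of trials at 75% correct and 50% DK, so it is not reliably conservative.

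Three stronger readings are tempting and not supported:

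- A reader might infer that missing the rule means the blind failed. The SAP says only when suitable blinding has been achieved; a miss withholds that label.
- A reader might infer that the verdict is mostly a matter of the DK share. At a fixed 30% DK, accuracy alone moves it from 98% to 0.5%. It depends on both.
- A reader might infer from the protocol's mention of active or sham only that DK was not offered, so that a perfect blind would almost never pass. That wording does not settle which options were recorded, and the SAP tabulates DK. The 0% case is a limiting case.

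**Conclusion.** The concern holds, with two distinct faults. The threshold is the SAP's own random-choice value, so a perfect blind earns 'suitable' in 28% of trials at 10% DK and 78% at 20%. The index combines DK share and accuracy, so one cut on it can pass a broken blind: 93% of trials when guessers are 75% correct and half answer DK.

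The percentages rest on the standard James formula, equal DK shares and 90 per arm; using 100 per arm changes them by at most about 5 points. The threshold argument needs only the SAP's own equation of 0.5 with random choice. The consequence is for interpreting the trial: type I error, power and the success criteria are untouched. The rule should be changed, but the trial's efficacy conclusion does not hang on it.

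**What to change.** In SAP 12.4, delete the sentence that makes a lower limit above 0.5 the verdict. Keep the James index and its interval as a description. From the six-cell table already planned, with the 1-month answers still taking precedence:

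1. Report for each arm the DK share and the share correct among those who name an arm, with 95% intervals.
2. Report the between-arm difference in DK share, and the between-arm difference (active minus sham) in the share saying 'active' among those who name an arm, each with a 95% interval (for example Newcombe).
3. Conclude that guesses track allocation if the interval for the second difference lies above 0.
4. State that an interval including 0 does not show that the blind held.
5. State which response options the app and the 6-month form recorded.

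Bang indices by arm are optional.

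With the Newcombe interval and 90 per arm, step 3 raises a false flag in 2.3–2.6% of trials at equal DK shares from 0 to 60%. It flags 75% correct guessing at 50% DK in 99.9% of trials. It is weaker for modest unblinding: 60% correct is flagged in 68% of trials at 20% DK and 48% at 50%.

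Step 4 is needed because a near miss remains compatible with real unblinding. At 20% DK, 90 × 0.80 = 72 per arm name an arm. If 42 against 31 say 'active', the difference is 15.3 points with interval −1.0 to 30.5. When accuracy is the same in both arms, the share correct is (1 + difference)/2, so the upper limit is (1 + 0.305)/2, about 65% correct. At 50% DK, 45 per arm name an arm. If 27 against 18 say 'active', the interval is −0.6 to 38.3 points, up to about 69% correct.

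The cost is SAP wording and a few table rows. No new data are needed and recorded answers are unaffected. The sponsor gives up a single pass/fail statement on blinding.

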## 13. CHANGES OF ANALYSIS FROM PROTOCOL

The analyses contained within this statistical analysis plan supersedes the analyses defined in the study protocol (May 26th 2019, Version 5). For clarity, a summary of deviations from the protocol are summarized, along with justification for the change.

Neurovalens Limited Identifier: EXP18020

Clinical Study Identifier: 243973

1. All terminology reference to treatment dose has been removed as subjects will not receive a specific dose of treatment, but rather use the device headset as demonstrated. The dose response analysis described in the protocol will be reference as a treatment response analysis within this statistical analysis plan and related documents thereafter. Additionally, the treatment response analysis (section 12.3) will be performed on the safety analysis set to reflect the treatment that subjects actually received as opposed to the Intention to treat population referenced in the protocol which reflects randomized treatment.

- 2. The protocol references using usage time as a covariate in the linear modelling of percentage fat loss from baseline. As a post baseline endpoint, it may be difficult to distinguish the relationship between percentage fat loss and usage time, due to a cause and effect relationship e.g. the subject may discontinue treatment as they think the treatment is not effective, which in turn means that their percentage fat loss is reduced. As a result, only baseline covariates will be used to adjust the percentage fat loss from baseline, in the same way that percentage weight loss from baseline is treated. As an alternative means of investigating the relationship between usage time and percentage weight or fat loss, a descriptive summary will be provided for weight and fat loss by categorical groups of usage adherence.
- 3. The protocol states that the demographic and baseline characteristics of subjects will be compared statistically between treatment groups. Owing to the sample size, statistical comparisons between treatment groups may highlight potential differences between groups which are not considered clinically different. For example, a 1 year age difference between treatment groups may be statistically significant but not clinically relevant. As an alternative the demographic and baseline characteristics of subjects will be summarized per treatment group and a clinical review of the differences between groups performed. Additionally, the primary efficacy endpoints utilize a linear model with demographic and baseline covariates included. This is considered a more powerful test, having accounted for baseline attributes, and will be performed as the primary analysis, with the t-test performed as a secondary and supportive efficacy analysis.
- 4. The protocol states that Adjustment of medication, both reduction and new medications will be summarized and included as an efficacy endpoint. The monitoring of medications can be a complex process due to changes to medication dose, frequency, brand etc. As a result, this analysis will summarize any increase, decrease, or no change in medication, as specified by an investigator during the course of study follow up. Additionally, the medication review will focus on diabetic and cardiovascular medications only as they are considered most relevant to the co-morbidities associated with being overweight or obese. Medications will also be summarized by treatment according to potential impact on weight status. These will be classified as medications that could potentially cause either weight gain or weight loss as deemed by the Chief Investigator.
- 5. The dietary endpoint total calorie intake is intended to form the basis of potential future labeling claims. The total calorie intake endpoint will inform on the quantity of food eaten.

#### **Neurovalens Limited**

Identifier: EXP18020 Clinical Study Identifier: 243973

While broadly comparable (see: https://www.ncbi.nlm.nih.gov/pmc/articles/PMC5690458/) and producing the same outcome measures, the two-day 24-hour dietary recall and FFQ look at quite different timespans. So, while the two-day 24-hour dietary recall is self-explanatory the FFQ analyses diet over the previous year. The FFQ will only be administered at baseline. Thus, for the analyses that will be used to derive total calorie intake as the basis of potential labelling claims the two-day 24-hour dietary recall will be used.

- 6. The protocol states all analyses will be conducted using the latest version of R. However, the analyses will be conducted in SAS®.
- 7. The protocol states that a t-test will be performed for each of the secondary endpoints used to form the basis of labelling claims. However, these endpoints will instead be analysed utilising a linear model adjusted for subject's baseline covariate of the particular endpoint being analysed and gender (stratification factor), which is a more powerful test accounting for baseline differences. T-test will be provided as supportive analyses
- 8. HEI score had been included as a secondary endpoint to form the basis of labelling claims in the protocol but has since been removed as a study endpoint. This change will be reflected in any future iterations of the protocol.
- 9. After discussion between the sponsor and the responsible FDA panel chair, it was decided that the study now comes to an end when the 6-month primary endpoint is reached. This means that there will no longer be an unblinded period of 6 months usage at the UCSD sites following this. This was decided in order to allow the UCSD sites to prioritise study visits in the blinded study phase which were strained as a result of the COVID-19 pandemic. All analyses relating to later time points than 6-months have been removed. This change will be reflected in any future iterations of the protocol.
- 10. An additional mentoring support company called Clinical Trial Mentors (CTM) has been added to assist with the lifestyle modification support that We Slim Together (WST) currently provides if required. This was put in place as a fallback option to allow for the continuation of mentoring support should the COVID-19 pandemic cause WST to be unable to deliver their mentoring service.
- 11. A new research site called Texas Endocrinology and Diabetes (TDE) in Austin was added to the trial in order to increase the recruitment pool as the COVID-19 pandemic strain

